1.2 Hypotheses

Related to Aim 1, we hypothesize that:

H1: Patients receiving the EMC2 intervention will have better understanding of medication risks than those in the control arm.

H2: Patients receiving the EMC2 intervention will demonstrate safer use of their medication than those in the control arm.

STU#: 00201638

H3: Adverse drug events will have a higher rate of detection for patients in the EMC2 intervention arm than in the control arm.

Related to Aim 3, we hypothesize that compared to usual care, patients receiving the EMC2 strategies will:

H4: Report higher rates of provider Rx counseling

H5: Report higher rates of receipt of print Rx information.

H6: Be more likely to communicate Rx questions.

H7: Report a greater frequency of clinic follow-up.

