9.4 Data Sources

Data sources for this study will include phone interviews with participants, data from participant responses to the IVR call, and survey responses from providers.

Data collected. The following measures, including covariates, effectiveness and fidelity outcomes, are described below.

Patient Covariates. Baseline assessment will include socio-demographics, social support, English proficiency, country of origin, health status, including number of comorbidities, and cognitive function (assessed by the Mini-Mental Status Exam). We will also probe for medication concerns (i.e. about costs, side effects, risks) for patients who do not fill or are not taking their medicine. We will assess health literacy via the Newest Vital Sign (NVS). Patients are given a copy of a nutrition label and asked 6 questions about how they would interpret and act on the information. Scores are classified as high likelihood of limited literacy (0-1), possibility of limited literacy (2-3), and adequate literacy (4-6). The NVS has a high correlation with the Test of Functional Health Literacy in Adults (TOFHLA) takes less time to administer, is validated in Spanish and includes numeracy items.

Patient Motivation. The Consumer Health Activation Index (CHAI) assesses participants' 'activation' or motivation to participate in healthcare decisions and actions.

Effectiveness Outcomes: Medication Knowledge. Medication-specific knowledge measures will be created per high-risk medication. Similar items will be made standard across drugs, related to 1) decision making prior to use, 2) risks and benefits, and 3) side effects. Correct answers will be

STU#: 00201638

tailored to the available content included in each Med Guide Summary, as done previously by our team. Total scores range from 0-100, calculated reflecting the % correct of total possible points for each medication.

Medication Behavior. We will assess medication behavior by three domains: fill, proper use, and actual use.

- Fill will be assessed by patient self-report (yes/no) of having attained the medication from the pharmacy.
- Proper Use, measured as yes/no per medication, will be assessed by requiring patients to properly indicate the correct indication, dose (# pills each time), frequency (times per day), and total pills per day.
- Adherence will be measured via the ASK-12 that includes 12 items assessing general medication attitudes and beliefs as well as, specific behaviors within the past 3 months.

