Adverse Drug Events (ADE). ADEs will first be assessed using a validated questionnaire administered by the RA during the 3-month follow-up phone call. If the patient reports that their medication is finished at the 1-month interview, the ADEs will be assessed using the same approach at the 1-month interview. [name] will review all self-reported ADEs to determine whether these symptoms could reasonably be linked to one of the prescribed high-risk medications. We will then determine whether confirmed ADEs were reported to the clinic via the IVR system by reviewing IVR data. Drs. [name] and [name] will oversee this process.

Fidelity Outcomes:

- Provider Counseling. We will ask patients (yes/no) whether their prescriber/nurse/pharmacist counseled them. We will also ask the Health Literacy supplemental items of the Consumer Assessment of Health Providers Survey (CAHPS) to evaluate the extent and quality of provider verbal counseling on Rx medications. Prescriber/nurse counseling will be assessed immediately following the appointment (during the baseline interview); pharmacist counseling will be assessed at baseline if the prescription has been filled by that time, otherwise on the 4-week call.
- Receipt of Med Guide Summaries. We will ask patients in both arms whether they received any written information from their provider.
- Receipt of IVR Calls and Nurse Counseling. We will collect data from the IVR to determine whether interviews were completed and whether responses warranted nurse counseling.
- Frequency of Clinic Follow-Up. We will ask patients (yes/no) whether someone from the clinic contacted them following any concerns reported to the IVR system.
- Helpfulness of EMC2 components. Intervention patients will be asked (yes/no) whether they received Med Guide Summaries, IVR calls, and follow-up nurse calls and how helpful they were. "On a scale of 1 to 10, 1 being not helpful at all and 10 being extremely helpful, how helpful was...?"
- Provider experience. We will ask providers at intervention clinics about their use of the BPA pop-ups (if they saw them and if so, how they used them), med sheets (if they noticed patients receiving them), and IVR (if they received any feedback from the patients about the call and if they saw any of the IVR reports).

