11. DATA AND SPECIMEN MANAGEMENT

11.1 Data analysis plan

Aim 1 Analysis Plan. The proposed trial uses a cluster-randomized design where the practice location is the unit of randomization. We will randomize 12 locations to two arms (usual care, EMC2) resulting in 6 per arm. Locations will be matched by total number of patients eligible for the study as well as proportion of Spanish speaking patients, with one location from each pair randomized to each arm. We will accrue ~100 patients per location, on average, and conservatively anticipate ≥80% retention at 3-month follow-up. These estimates result in 1200 participants recruited with an anticipated 960 patients (480 per arm, 80 per location) available for primary data analysis.

Medication knowledge associated with high-risk medications is the first primary outcome of interest for Aim 1 (H1), and will be analyzed as a score ranging from 0-100 reflecting the percent of items correct for each medication. Medication use outcomes (proper use, adherence) and detection of ADEs are relevant to the other hypotheses of interest for Aim 1 (H2, H3). Associations between the outcomes and potential confounders at the patient (socio-demographic characteristics, comorbidities, # and type of medications taken, previous history with side effects, literacy, and primary language) and medication (drug type, route of administration) levels will be examined. We intend to use generalized linear mixed models (GLMM) to analyze the data, which can handle data that is missing at random (MAR). Additionally, we will examine rates of missing data, and determine if there are any discernible patterns using GLMMs with a logit link function to predict the presence of missing data. Should we find significant predictors, we will use multiple impute methods and present results as secondary analyses.

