11.2 Power analysis

The sample size for this study was based on comparisons of the primary outcome of medication knowledge between the two arms (i.e., usual care vs EMC2) at the 3-month interview. We expect

STU#: 00201638

participants in the usual care arm to score an average of 55.6 (SD=28.4) based on a previous study testing comprehension of the FDA standard Med Guides to those to be used in this study. Enrolling 1200 participants and estimating 80% retention at the follow-up interview (n=960, 480 per arm), we will have 80% to detect a minimum difference of 5.5 between the EMC2 and the usual care arm assuming a Type I error of 5%, assuming 100 patients per practice site enrolled at baseline and n=80 available at 3 month follow-up. This effect size was calculated based on an independent t-test with a variance inflation factor to account for the cluster-randomized design. An intra-class correlation coefficient (ICC) of 0.001 was used as we expect the clustering of practice site to have minimal influence on patient outcomes.

Usual care estimates for understanding of risks and demonstrated safe use outcomes were obtained from prior work. For subgroup analyses on these outcomes for Aim 2, we expect roughly 38% to have limited health literacy. Detectable differences at 3 months are based on estimates of 3 patients per provider with limited literacy and 5 with adequate literacy. Detection of ADEs is defined as the number of events recorded in the medical chart out of the total number reported by patients at the 3-month interview. In a study in which 20% of participants reported at least 1 adverse drug event, 35 of their 166 (21%) reported events were recorded in their medical chart. Therefore, the sample size calculation for this outcome was based on 21% of reported ADEs in 20% of our expected sample at 3 months (n=96 per arm, 3 patients per 32 providers, assuming an equal number of providers in each arm will have patients with no ADEs). We will be able to detect a minimum of 18.2 between the EMC2 and the usual care arm. For subgroup analyses by literacy, we assume 1 patient per provider with limited literacy and 2 with adequate literacy.

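### ADE detection (H3) is defined from charts in 11.2 but checked from IVR data in 9.4, with no stated usual-care source; separately, the H7 item as described has no meaningful usual-care answer

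*Combined protocol and SAP*

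**What the plan says.** Section 1.2 states H3 as a between-arm comparison: "Adverse drug events will have a higher rate of detection for patients in the EMC2 intervention arm than in the control arm". Section 11.1 places ADE detection among the Aim 1 outcomes, to be analysed by mixed models with a logit link for binary outcomes and practice location as a random effect.

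Section 11.2 gives a definition: "Detection of ADEs is defined as the number of events recorded in the medical chart out of the total number reported by patients", with the reports taken at the 3-month interview. It takes a 21% base rate (35 of 166 events) from an earlier study and gives a detectable difference of 18.2 with 96 per arm.

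Section 9.4 describes the measurement differently. ADEs come from a questionnaire at 3 months. If the medicine is finished at 1 month, "the ADEs will be assessed using the same approach at the 1-month interview". A reviewer "will review all self-reported ADEs to determine whether these symptoms could reasonably be linked to one of the prescribed high-risk medications". Then: "We will then determine whether confirmed ADEs were reported to the clinic via the IVR system by reviewing IVR data". No other check of detection is described. On sources, the same section says: "Data sources for this study will include phone interviews with participants, data from participant responses to the IVR call, and survey responses from providers". Section 25.3 states that the research team will not see medical records.

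For H7, section 1.2 predicts that EMC2 patients will, compared with usual care, "Report a greater frequency of clinic follow-up". The item described in 9.4 is a yes/no question on whether the clinic made contact after a concern the patient had reported to the IVR. The Aim 3 plan in 11.1 compares H4 to H7 between arms with simple bivariate tests.

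**The concern.** A between-arm test needs a measure that can be obtained in the same way in both arms. For H3, the definition behind the sample-size figure (charts) has no described means of collection, and the check that is described (IVR data) relates to a tool given to one arm. An analyst following the text could not compute usual-care detection without inventing a source, and two analysts could reasonably invent different ones.

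At stake are the interpretation of one of the three Aim 1 hypotheses and the relevance of its precision figure. H7 has a similar but separate problem: the question presupposes exposure to an intervention component.

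**Working it through.** **1. Reproduce the plan's figure.** Inputs from 11.2: usual-care rate p1 = 0.21; 96 per arm (20% of 480). The 80% power and 5% type I error are stated there for the knowledge outcome. I assume they carry over, two-sided, and that 18.2 means percentage points. Clustering is ignored.

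The detectable difference solves d = (1.960 + 0.842) × √{[p1(1 − p1) + p2(1 − p2)]/n}, with p2 = p1 + d.

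- At p2 = 0.392: 0.21 × 0.79 + 0.392 × 0.608 = 0.1659 + 0.2383 = 0.4042.
- 0.4042/96 = 0.004211; the square root is 0.0649.
- 2.802 × 0.0649 = 0.182. Solved exactly, d = 18.18 points.

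The pooled-variance version gives 18.46 points, and 79% power at 18.2 points. The arithmetic is sound. The 96 counts patients, whereas the 21% counts events.

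**2. Set the two descriptions side by side.**

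| Element | 11.2 | 9.4 |
|---|---|---|
| Numerator | Event is in the chart | Event was reported through the IVR |
| Denominator | All patient-reported events | Events the reviewer links to a study medicine |
| Time point | 3 months | 3 months, or 1 month if the medicine is finished |
| Usual care | Charts exist; no extraction described | No IVR |

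The 21% and the 18.2 points belong to the 11.2 column only.

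**3. Look for a usual-care source.**
- Sections 9.1 and 9.3 make the IVR part of the intervention and prompt only that arm to call. Usual care has no active post-visit surveillance.
- The source list in 9.4 has no charts.
- The Alliance feed described in 3.1 carries contact details, language and visit date and, under Method 2, medicine, sig and prescriber or physician names. It has no ADE content.
- No interview item is described that asks either arm whether the clinic learned of an ADE.

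**4. If only the 9.4 check were used.** Usual care would have 0 detected events whatever its clinics knew. Its log-odds would be log(0), so the logit model in 11.1 would have no finite estimate of the arm effect. The 21% base rate could not apply.

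**5. Timing.** One IVR call is described, prompted the day after baseline. The final interview is 4 + 8 = 12 weeks after baseline. An ADE that begins after the call cannot appear in the IVR data, even in the EMC2 arm.

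**6. H7.** Usual-care patients have no IVR to which they could report a concern. Their answers would be missing or an automatic no, so the planned between-arm test would not measure clinic follow-up.

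**The case against.** The best defence is that 11.2 is the definition and 9.4 describes only the part of it that comes through the IVR. Section 9.2 has flagged IVR concerns appear in the chart as a lab report, so the numerators overlap. Charts exist in both arms, Alliance already sends EHR data, and the no-access sentence closes a section about recruitment data. On this reading only an extraction procedure is missing.

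Much of that stands. A reader might infer that charts are ruled out, but the source list does not claim to be complete and an Alliance extract is not excluded. A reader might also infer that H3 will be scored from IVR data alone and so will yield a guaranteed positive. Section 9.4 does not say so, and the planned model would break down at zero usual-care events rather than return a simple significant result.

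The defence does not supply the missing source, however. It also leaves open whether an automatically posted lab report counts by itself as detection, and it does not reconcile the denominators or time points.

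On H7, the questionnaire is not in the documents, and the objection that a one-line description may not be its exact wording is fair. The point concerns the item as described.

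**Conclusion.** The inconsistency is real and should be fixed. H3 has two non-matching measures and no stated usual-care source, and the H7 item as described cannot support the comparison planned for it. The 18.2-point figure is correct arithmetic for a chart-based measure with all reported ADEs as denominator, and for nothing else.

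The scope is limited. Section 8 names knowledge and medication behaviour as primary and lists ADEs under safety endpoints; the primary knowledge endpoint is unaffected.

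Two further inferences are not supported. Restricting the denominator to confirmed ADEs might suggest a calculable loss of power, but the plan gives no confirmation rate, and a rate per event cannot be applied directly to a count of patients. The long interval after the IVR call might suggest that most ADEs are missed, but the documents do not say when ADEs begin, so elapsed time does not give a share of events.

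**What to change.** State one definition of detection (numerator, reported or confirmed ADEs as denominator, time point including the 1-month branch) and one source used in both arms. Make the source list and ADE text in 9.4, the definition in 11.2 and the access statement in 25.3 agree. Two routes are open.

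- **Interview item.** In the existing ADE interview, ask both arms for each ADE whether the clinic learned of it and by which route. Report results with and without the IVR route, since leaving it out removes the intervention's own mechanism.
- **Alliance chart extract.** List it for both arms, confirm that consent and HIPAA authorization cover it, and state whether an automatically posted IVR lab report counts as detection.

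Under either route, keep the IVR count as a fidelity measure in the EMC2 arm. Restate or drop the 21% and 18.2-point figures unless the definition is chart-based with all reported ADEs as denominator. For H7, ask both arms whether anyone from the clinic has contacted them about the medicine since the visit.

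The interview changes cost one or two questions, Spanish translation and an IRB modification. Patient-reported clinic awareness is softer than chart data, may be primed in IVR callers (who are told that issues go to their clinic), has no base rate for power, and will be missing for patients already past the ADE interview. This route needs interviews still to be running. The extract also needs an IRB modification and must be arranged before identifiers are deleted at study completion (11.3).

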- EHR Tools to Deliver Patient Medication Information. Drs. [name] and [name] continue to work together on several pilot projects that leverage EHR platforms (EpicCare, Cerner Powerchart, GE Centricity) to standardize prescribing, provide Spanish translations, prompt medication reconciliation before and during clinical encounters, and to automatically generate Med Guide Summaries (Epic, Cerner, Centricity). Med Guide Summaries are embedded in the EHR as PDF documents, linked to medications, and automatically cued to print with the after-visit summary once a prescriber places the order. As each Med Guide Summary was written in active voice, it also serves as a counseling support tool. In prior field tests [R18HS17220; R21CA132771], each PDF Summary had a 'dot phrase' function so a provider could manually access and share content on screen by simply typing the name of the drug and hitting return (i.e. ".REGLAN <ENTER>"). While >85% of the time patients received Med Guide Summaries, the dot phrase commands were too passive as a method for providers to use for counseling. Guided by Alliance clinical staff feedback, the EMC2 now will use a prescriber alert to prompt clinicians and automate a view of the Med Guide Summary, with an option to 'ignore' if desired.
- Training Clinicians on Health Literacy Spoken Counseling Best Practices. Collectively, Drs. [name], [name] and [name] have extensive experience developing and implementing provider and nurse training sessions for brief counseling to support preventive screening, disease management, hospital discharge instructions, and medication education.

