9.1 Study design

We will conduct a 2-arm, randomized trial at one Alliance-affiliated federally qualified health center (FQHC) in Chicago, Near North Health Services Corporation, to evaluate the EMC2 intervention strategy compared to usual care.

We will assess patients' Rx knowledge and behavior at baseline, 4 weeks, and 3 months. Prevalence of ADEs and rate of their detection will be determined at 3 months or at an earlier interview if they state having already completed the course of medication. The fidelity and economic impact of the intervention will also be investigated via process and cost measures, in addition to patient and provider feedback. Results will determine effectiveness and identify any necessary modifications, guiding future dissemination efforts.

Study Arms:

Usual Care. Current usual care includes 1) variable physician and/or nurse counseling without any EHR notifications or counseling support; 2) no distribution of print medication information materials in Alliance clinics, and variable, limited distribution likely in pharmacies; 3) no active surveillance of medication use post-visits.

Intervention Arm: EMC2 Strategy. Following a patient's movement through a provider visit at one of the Near North clinics randomized to the intervention, the following five activities (described in more detail in 9.2) will occur:

- Provider counseling (prompted by provider medication alert)*
- Automated delivery of med guide summary*
- IVR follow-up phone assessment
- IVR lab report to clinic via EHR
- Nurse counseling (if warranted by lab report)

**Because the first two activities must occur at the time of the clinic visit, which is before we will have the opportunity to invite the participant to enroll in the study, those activities will occur for all patients prescribed a study medication at an intervention clinic, regardless of whether or not they subsequently enroll. (see last paragraph of 3.1)*

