To account for the correlated nature of the data from participants at the same practice and multiple observations per patient, we will use GLMMs for analyses of all data, specifying identity link for continuous and the logit link for binary outcomes using PROC GLIMMIX in SAS (v.9.4). Treatment assignment by time will be the independent variable of primary interest and modeled as a fixed effect and practice location as a random effect, with additional subject statement to model correlations within patient. We will also include fixed effects for any potential confounding covariates noted in the descriptive studies. For all GLMM analyses we will report point estimates and 95% confidence

STU#: 00201638

intervals, and the extent to which random effects suggest correlation of outcomes within practice location. Additionally, we will estimate the ICCs for all outcomes to be used in future studies.

Aim 2 Analysis Plan: We will repeat all GLMM analyses described in Aim 1, but with the inclusion of a fixed effect for participants' literacy defined as limited (inadequate or marginal literacy) vs. adequate. We will formally test for differences in intervention effects according to literacy by including a literacy-intervention interaction term. Statistically significant interaction terms ($p < 0.05$) will indicate that the disparities in understanding between the intervention and usual care group vary by literacy level. Similar analyses will be used to test for interactions of intervention effects by age and English proficiency (using Census criteria of 'very well' vs. 'less than very well').

Aim 3 Analysis Plan: Following completion of enrollment, we will determine the extent to which the intervention was implemented as planned in the intervention arm. We will ask patients in the intervention arm if they were counseled, and whether they received the Med Guide Summaries and the post-visit IVR call. Bivariate analyses will be performed to compare relevant outcomes for H4-H7 between arms using t-tests, Wilcoxon Rank-Sum, or χ^2 tests, as appropriate. Aim 3 findings will also directly inform follow-up qualitative investigations in Aim 4.

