Aim 5 Analysis Plan: We will directly measure and assess the provider perspective costs of developing and running the EMC2 Strategy. Specifically, we will estimate the incremental cost of the intervention relative to usual care from the perspective of the Alliance and each FQHC implementing this process and tools. The primary costs of running the EMC2 Strategy involves the limited expenses around printing (printer ink, paper, staff time) as a result of generating new medication information with after-visit summaries. However, we will include estimates for minimal programming maintenance, for both GE Centricity EHR and the IVR system, and will test the sensitivity of results to changes in the maintenance requirements in terms of programmer hours. We also will separately track development costs for software and other programming requirements based on programmer hours. Staff/programmer costs will be measured using tracked time spent on the intervention and wage estimates. We will test the sensitivity of operational costs to different assumptions about the potential use of variable staff using different salaries but assuming the same proficiency in terms of time required. Further, we will assess the sensitivity of estimates to different proficiency levels that could arise from learning by doing.

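### H5 is about printed prescription information, but the only receipt measure described for both arms covers written material of any kind, so the arm difference may be biased toward zero

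*Combined protocol and SAP*

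**What the plan says.** Section 1.2 states the hypothesis, relative to usual care, as "H5: Report higher rates of receipt of print Rx information". It does not name the Med Guide Summary.

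Section 9.4 lists a fidelity outcome headed as receipt of Med Guide Summaries and defines it so: "We will ask patients in both arms whether they received any written information from their provider". A later entry in the same list, on helpfulness, names the sheet but covers one arm: "Intervention patients will be asked (yes/no) whether they received Med Guide Summaries, IVR calls, and follow-up nurse calls and how helpful they were".

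The Aim 3 plan in section 11.1 asks intervention patients "whether they received the Med Guide Summaries and the post-visit IVR call", and then compares the arms on H4 to H7 with bivariate tests. It names no other measure for H5.

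Section 9.1 describes usual care as "no distribution of print medication information materials in Alliance clinics, and variable, limited distribution likely in pharmacies". Two places mention after-visit summaries. Section 2.2, on the team's pilot work, says the sheets are "automatically cued to print with the after-visit summary once a prescriber places the order". The Aim 5 plan in section 11.1 counts "limited expenses around printing (printer ink, paper, staff time) as a result of generating new medication information with after-visit summaries".

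The documents give no expected rate or power for H5 and do not reproduce the interview questionnaire.

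**The concern.** Three things that should agree do not. The hypothesis is about printed prescription information, the outcome's heading is about the Med Guide Summary, and the measure as described is about written material in general. Followed literally, the plan would score an appointment slip, a referral sheet or an after-visit summary as a success for H5.

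That matters most in usual care. Section 9.1 puts clinic distribution of print medication information there at none, so every yes based on clinic paper would be a false positive. In the intervention arm most patients should truly have the sheet, which leaves less room for false positives. If the tendency to answer yes is similar in the two arms, the difference shrinks.

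Aim 3 reports whether the strategy delivered what it was meant to deliver, and Aim 4 follows up the gaps it finds. A usual-care rate well above zero would misdescribe the comparator and contradict section 9.1. An understated difference would misreport how much print delivery EMC2 added.

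**Working it through.** There is no stated figure for H5 to reproduce, so this is a misclassification calculation on stated assumptions.

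**Inputs**
- True receipt, intervention: 0.85. Section 2.2 reports more than 85% in earlier field tests; 0.50 serves as a low scenario (assumption).
- True receipt from the clinic, usual care: 0, from section 9.1.
- a: the share of patients without printed prescription information who still answer yes. Not in the documents; varied as an assumption.
- 600 patients per arm (section 23); ICC 0.001 and type I error 5% (section 11.2), taken as two-sided; 100 patients per site (section 11.2).

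**Formula.** Observed rate = p + (1 − p)a in each arm. With equal a, observed difference = (p_T − p_C)(1 − a), here 0.85(1 − a).

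| a | Intervention | Usual care | Difference |
|---|---|---|---|
| 0 | 85% | 0% | 85 points |
| 0.2 | 88% | 20% | 68 points |
| 0.5 | 92.5% | 50% | 42.5 points |
| 0.8 | 97% | 80% | 17 points |
| 0.9 | 98.5% | 90% | 8.5 points |

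Both rates rise, but unevenly: at a = 0.5, intervention gains 7.5 points and usual care gains 50.

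**Unequal shares.** Write a_T for the share in the intervention arm and a_C for usual care. The difference is then 0.85 + 0.15a_T − a_C. With a_T = 0.8 and a_C = 0.5 it is 0.85 + 0.12 − 0.50 = 47 points. With a_T = 0.5 and a_C = 0.8 it is 0.85 + 0.075 − 0.80 = 12.5 points. The difference is understated whenever a_C exceeds 0.15a_T. It would be overstated only if false positives were far rarer in usual care.

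**Does the test fail?** Design effect = 1 + (100 − 1)(0.001) = 1.099, so effective n = 600/1.099 ≈ 546 per arm.
- True receipt 85% vs 0%: power stays above 99% up to a = 0.9 and is 98.8% at a = 0.95.
- True receipt 50% vs 0%: the difference is 10 points at a = 0.8 (power 99.7%), 5 points at a = 0.9 (88%) and 2.5 points at a = 0.95 (58.5%).

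These powers ignore the small number of clinics (seven in sections 3.2 and 19.1, twelve in section 11.1). A cluster-level test would have less.

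**The case against.** The strongest reply is that section 9.4 summarises a measure and is not the questionnaire. The entry sits under a heading about the Med Guide Summary and follows one on prescription counselling. Under the second screening method in section 3.1, the interviewer can tell the patient which medicine is meant. The cognitive interviews with 30 patients in section 9.3 could expose a vague question. The administered item may therefore be specific. That stands as a possibility, but the plan does not say so, and it describes no other item that could test H5.

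Second, a reader might infer that usual-care receipt is in fact overstated because those patients are handed after-visit summaries. The documents do not support that. Section 2.2 describes pilot projects, section 9.2 describes printing at checkout without mentioning an after-visit summary, and Aim 5 only implies that such summaries exist. How often usual-care patients receive one is not stated.

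Third, a reader might infer that a null Aim 1 result could not be traced to failed delivery. That also goes too far. Intervention patients are asked about the sheet by name, and providers are surveyed on whether they noticed patients receiving it. Within-arm delivery can be estimated without the disputed item. What remains is that the patient evidence is recall. Section 9.2 puts the baseline interview 1 to 30 days after the visit, while the 2-to-45-day IVR window in section 9.3 implies up to 44. Section 9.4 does not say at which interview the written-information item is asked.

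**Conclusion.** The mismatch between H5 and its only described two-arm measure is real and should be corrected. As written, the measure can count paper unrelated to medicines, may raise reported receipt in both arms and more so in usual care, and so may bias the difference toward zero. With true rates of 85% and 0% and equal a, the difference reads as 68, 43 or 17 points at a = 20%, 50% or 80%. These figures illustrate the size of the problem: a is assumed, 85% comes from earlier field tests, and the exact shrinkage needs equal a in both arms.

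It would be wrong to conclude that H5 will be missed. A lost test becomes likely only with very high a and low true delivery together, subject to the caveat on few clinics. The damage is to the effect size and the usual-care rate. H5 is a fidelity comparison, and the primary endpoints are not affected.

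**What to change.** 1. Ask both arms the same question: did the clinic give you any printed information about [named study medicine], such as its risks, side effects or safe use, either alone or with other visit papers? The last phrase matters. If the sheet prints together with an after-visit summary, asking about a sheet apart from that summary would invite false no answers from intervention patients.
2. Ask separately about other visit paperwork and about pharmacy leaflets.
3. Name the medicine-specific item as the H5 outcome in sections 9.4 and 11.1. Keep the intervention-only item for within-arm fidelity.
4. Optionally, report the Centricity print-cue record beside patient recall for intervention patients. It shows that a print was cued, not that the patient received it.

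Items 1 to 3 cost one reworded question, short added questions in English and Spanish, and a protocol edit. Item 4 depends on whether Alliance can supply the field and on consent and IRB terms, since section 25.3 gives the research team no access to medical records. The first three stand without it.
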